#### Recommended Maximum Daily Dose of Statins for Subjects Randomized to Roxadustat

Statins	Recommended maximum dose (mg/day)
Atorvastatin	40
Simvastatin	5
Rosuvastatin	5
Pravastatin	40
Fluvastatin	20
Pitavastatin	1
Lovastatin	20

#### 4.6.2 Supplemental Iron Use

In a Phase 2 study, there was no significant difference in Hb levels in roxadustat-treated subjects on dialysis receiving oral iron supplementation compared to subjects receiving IV iron supplementation, in subjects with ferritin < 100 ng/mL and in those with TSAT < 20%. Based on the mechanism of action of roxadustat and the Phase 2 study results, in subjects randomized to roxadustat, oral iron supplementation is considered to be sufficient.

In this study, oral iron should be allowed as the preferred first-line of iron supplementation for both treatment arms without restriction.

In addition to scheduled assessments (Appendix 3), iron indices may be assessed anytime (via central lab) to evaluate iron storage status of the subjects, if considered necessary by the Investigator.

##### 4.6.2.1 Oral Iron Supplementation

All subjects should be encouraged to take oral iron if they can tolerate as the preferred first-line iron supplementation during the Treatment Period. Provision of an oral iron supplement is encouraged; the dose and frequency are at the discretion of the principal Investigator. Oral Iron therapy should be started before the subject becomes iron depleted.

#### 4.6.2.2 Intravenous (IV) Iron Supplementation

Intravenous iron supplementation is permitted if in the opinion of the Investigator the subject has not responded adequately and is considered iron deficient. IV iron may be administered per local standard of care as deemed necessary by the investigator.

Treatment with study medication (roxadustat or epoetin) will continue during IV iron administration. Discontinuation of IV iron supplementation is recommended once the subject is no longer considered iron deficient (eg, ferritin  $\geq$  100 ng/mL and TSAT  $\geq$  20%)

Subjects may receive IV iron during the post-treatment Follow-up Period per discretion of the Investigator. If IV iron is to be administered at the EOT visit, all visit procedures including lab draws should be completed prior to administering IV iron.

#### 4.6.3 Rescue Therapy Guidelines

Rescue therapy guidelines are provided to optimize the standardization of rescue therapy by Investigators and to ensure the safety of individual study subjects. Use of rescue therapy and reason for rescue therapy should be recorded in the electronic case report form (eCRF).

##### 4.6.3.1 Red Blood Cell Transfusion (all subjects)

For subjects in both treatment arms, RBC transfusion is allowed if rapid correction of anemia is required to stabilize the subject's condition (eg, acute hemorrhage) or the Investigator is of the opinion that the blood transfusion is a medical necessity. If the situation permits, the Medical Monitor should be informed prior to any scheduled RBC transfusion. Study treatment may continue during or after the RBC transfusion.

##### 4.6.3.2 Erythropoiesis Stimulating Agents

For subjects randomized to roxadustat the use of ESAs is generally prohibited. Erythropoiesis stimulating agent rescue is restricted to no more than one cycle of use during the Treatment Period; the Investigator may initiate use of an approved EPO analogue if all of the following criteria are met:

- A subject's Hb level has not sufficiently responded to two or more dose increases or the maximum dose limit of the study drug has been reached; and
- The subject's Hb is  $<$  8.5 g/dL on two consecutive measurements (central lab) drawn at least five days apart; and
- Clinical judgment does not suggest iron deficiency or bleeding as a cause of lack of response or rapid decline in Hb; and
- Reducing the risk of alloimmunization in transplant eligible patients and/or reduction of other RBC transfusion-related risks is a goal

The subject is not allowed to be administered both the EPO analogue and roxadustat at the same time. Treatment with an EPO analogue should be started  $\geq$  3 days after the last dose of roxadustat, and should be stopped when Hb  $>$  9 g/dL or after 4-weeks, whichever comes first. If a subject requires longer than 4-weeks therapy due to inadequate response the Medical Monitor should be contacted. Study treatment should be resumed after the following intervals:

- Two days after stopping epoetin
- One week after stopping darbepoetin alfa
- Two weeks after stopping methoxy polyethylene glycol-epoetin beta (Mircera®)

If more than one cycle of EPO analogue rescue is required, the Investigator should permanently discontinue roxadustat. Use of EPO analogues will be recorded in the eCRF.

Inadvertent ESA administration or ESA administration by the hospital staff in Roxadustat subjects should not be counted as rescue unless above criteria are met; these subjects may be allowed to continue taking study medication, if considered safe by the Investigator or Medical Monitor.

For subjects randomized to epoetin alfa, the Investigator may initiate use of a different EPO analogue if clinically indicated. Use of the different EPO analogue will be recorded in the eCRF and will be considered rescue therapy.

#### **4.6.4 Emergency Procedure (Therapeutic Phlebotomy)**

If there are clinical concerns for a subject's high Hb levels, the Investigator may decide to perform a therapeutic phlebotomy in addition to temporarily withholding the study drug. This should be documented and discussed with the Medical Monitor.

#### **4.6.5 Prohibited Medications/Therapies/Substances**

The following medications/therapies are prohibited during the period identified:

- Any investigational drug from 4 weeks prior to screening until EOS
- Androgens from screening until EOS
- Iron-chelating agents (eg, deferoxamine/desferrioxamine, deferiprone, or deferasirox therapy) from 4 weeks prior to randomization until EOS
- Dapsone (at any dose) from screening until EOS
- Chronic doses acetaminophen/paracetamol > 2.0 g/day from randomization until 1 week after EOT

#### **4.6.6 Contraception**

Female subjects of childbearing potential, if not practicing complete sexual abstinence, must agree to practice a dual method of contraception, for example, a combination of the following: (1) oral contraceptive, depo progesterone, or intrauterine device; and (2) a barrier method (condom or diaphragm). Male subjects (nonsurgically sterile; ie, no vasectomy) with female partners of childbearing potential who are not on birth control must agree to use a barrier method of contraception (eg, condom) or the female partner must agree to use contraception as described above unless practicing complete sexual abstinence.

Subjects must agree to practice above contraceptive methods, as applicable, for the entire duration of the study, from randomization through the EOS visit. It is highly recommended that they continue to practice the contraceptive methods for 12 weeks following the last dose of study treatment. For subjects discontinuing study medication prematurely, it is recommended that they continue to practice contraceptive methods for 12 weeks following the last dose of study treatment.

Pregnancy, spontaneous or therapeutic abortion, or events related to pregnancy must be reported (Section 8.3.6)

#### **4.7 Safety Monitoring Plan**

Safety will be assessed throughout the study. A complete baseline profile of each subject will be established through demographics, medical history, clinical laboratory values, vital signs, physical examination (PE), and electrocardiogram (ECG). During the course of the study, vital signs, PE, and laboratory tests will be performed at regular intervals as described in schedule of assessments (Appendix 3).

Blood pressure and HR should be assessed according to the guidelines described in Appendix 5.

A comprehensive PE will be conducted during the Screening visit, Day 1 and at the EOT/ET visit. Targeted PEs (eg, general appearance, CV, respiratory and abdomen,) will be conducted throughout the study as described in the Schedule of Assessments.

Any significant findings prior to administration of study drug will be considered as baseline conditions and if appropriate, will be captured as baseline medical history. Any clinically significant (CS) changes from baseline will be monitored throughout the study and appropriate interventions will be taken accordingly. Clinical laboratory tests may be assessed at additional times on unscheduled visits for safety reasons. Liver function abnormalities will be monitored according to drug-induced liver injury (DILI) guidance (Appendix 4).

All adverse events, SAEs, and ongoing concomitant medication usage will be monitored and recorded throughout the study. Serious adverse event reports will be evaluated individually to assess for the impact of the event, if any, on the overall safety of the product and on the study itself. Cumulative AEs will be monitored throughout the study. Serious adverse events and AEs will be followed until resolved, deemed stable, or until the subject's EOS visit. See Section 8 for details on AE and SAE reporting.

An Independent Event Review Committee (IERC), blinded to treatment group, will adjudicate prespecified CV, cerebrovascular, and thromboembolic safety events of interest. These events include all-cause death, MI, stroke, hospitalization for congestive heart failure, hospitalization for unstable angina, deep venous thrombosis, pulmonary embolism, and hypertensive emergency. A separate adjudication charter will describe the process in detail, and training and training materials will be provided to study sites.

#### **4.8 Data Safety and Monitoring Board**

A Data Safety Monitoring Board (DSMB) will review safety data at least every six months or twice per calendar year while the trial is ongoing to ensure subject safety. A separate DSMB charter will establish the rules, meeting frequency, and scope of responsibilities of the DSMB.

## 5 STUDY ENROLLMENT AND WITHDRAWAL

### 5.1 Inclusion Criteria

A subject is eligible for the study if all of the following criteria are met:

1. Subject has been informed of the investigational nature of this study and has given written informed consent in accordance with institutional, local, and national guidelines
2. Subject age is  $\geq 18$  years
3. Subject receiving adequate dialysis using the same modality of dialysis for native kidney ESRD for  $\geq 3$  months prior to screening and during screening
  - 3.1 **Amendment 2: Incident dialysis subjects receiving dialysis for ESRD for  $\geq 2$  weeks but  $\leq 4$  months at the time of randomization**
4. For subjects receiving HD, the vascular access must be via native arteriovenous fistula or graft, or permanent, tunneled catheter. For subjects receiving PD, a PD catheter must be in use
5. Subject is on IV or subcutaneous ESA for  $\geq 8$  weeks prior to screening. The prescribed ESA dose must remain stable ( $\leq 30\%$  change) during the 4 weeks prior to randomization if on epoetin or darbepoetin and 8 weeks if on Mircera®
  - 5.1 **Amendment 2: Incident dialysis subjects (as defined in 3.1) must be on ESA for  $\geq 4$  weeks prior to screening**
6. Mean of the subject's three most recent central lab Hb values during the Screening Period must be  $\geq 9.0$  g/dL and  $\leq 12.0$  g/dL; with an absolute difference of  $\leq 1.3$  g/dL between the highest and the lowest value. Samples are obtained at least 4 days apart and the last Hb value must be within 10 days prior to the randomization visit
  - 6.1 **Amendment 2: For Incident dialysis subjects (as defined in 3.1), mean of the subject's two most recent central lab Hb values during the Screening Period must be  $\geq 8.5$  g/dL and  $\leq 12.0$  g/dL; with an absolute difference of  $\leq 1.3$  g/dL between the highest and the lowest value. Samples are obtained at least 2 days apart and the last Hb value must be within 10 days prior to the randomization visit**
7. Subject has a ferritin level  $\geq 100$  ng/mL at screening

**Amendment 2:** Subjects with a ferritin level  $< 100$  ng/mL at screening may qualify upon receiving iron supplement (per local standard of care)
8. Subject has a transferrin saturation (TSAT) level  $\geq 20\%$  at screening

**Amendment 2:** Subjects with a TSAT level  $< 20\%$  at screening may qualify upon receiving iron supplement (per local standard of care)
9. Subject has a serum folate level  $\geq$  lower limit of normal (LLN) at screening

**Amendment 2:** Subjects with a serum folate level  $< LLN$  at screening may qualify upon receiving folate supplement (per local standard of care)

10. Subject has a serum vitamin B12 level  $\geq$  LLN at screening  
**Amendment 2:** Subjects with a Vitamin B12 level  $<$  LLN at screening may qualify upon receiving B12 supplement (per local standard of care)
11. Subject's alanine aminotransferase (ALT) and aspartate aminotransferase (AST) are  $\leq 3$  x upper limit of normal (ULN), and total bilirubin (TBL) is  $\leq 1.5$  x ULN at screening
12. Subject's body weight (dry weight in HD subjects) is 45.0 to 160.0 kg

**Only incident dialysis subjects who meet criteria 3.1, 5.1, and 6.1 (instead of criteria 3, 5, and 6) are allowed to participate under Protocol Amendment 2**

## 5.2 Exclusion Criteria

Subjects will be excluded if any of the following criteria are met:

1. Subject has received a red blood cell (RBC) transfusion within 8 weeks prior to randomization  
Amendment 2: Subject has received a red blood cell (RBC) transfusion within 4 weeks prior to randomization
2. Subject has a known history of myelodysplastic syndrome or multiple myeloma
3. Subject has a known hereditary hematologic disease such as thalassemia or sickle cell anemia, pure red cell aplasia or other known causes for anemia other than chronic kidney disease (CKD)
4. Subject has known hemosiderosis, hemochromatosis, coagulation disorder, or hypercoagulable condition
5. Subject has a known chronic inflammatory disease that could in the opinion of the Investigator impact erythropoiesis (eg, systemic lupus erythematosus, rheumatoid arthritis, celiac disease) even if it is currently in remission
6. Subject is anticipated to undergo elective surgery that is expected to lead to significant blood loss during the study period or anticipated elective coronary revascularization.
7. Subject has active or chronic gastrointestinal bleeding
8. Subject has received any prior treatment with roxadustat or another HIF-PHI
9. Subject has been treated with iron-chelating agents within 4 weeks prior to randomization
10. Subject has a history of chronic liver disease (eg, chronic infectious hepatitis, chronic auto-immune liver disease, cirrhosis, or fibrosis of the liver)
11. Subject with New York Heart Association (NYHA) Class III or IV congestive heart failure
12. Subject has had a MI, acute coronary syndrome, stroke, seizure, or a thrombotic/thromboembolic event within a major vessel (excluding vascular dialysis access) (eg, DVT or pulmonary embolism) within 12 weeks prior to randomization

13. Subject has uncontrolled hypertension, in the opinion of the Investigator, (eg, that requires change in anti-hypertensive medication) within 2 weeks prior to randomization
14. Subject has one or more contraindications for treatment with epoetin alfa or other ESA including known hypersensitivity
15. Subject has a diagnosis or suspicion (eg, complex kidney cyst of Bosniak Category II or higher) of renal cell carcinoma as shown on renal imaging performed within 12 weeks prior to randomization
16. Subject has a history of malignancy, except for the following: cancers determined to be cured or in remission for  $\geq 5$  years, curatively resected basal cell or squamous cell skin cancers, cervical cancer in situ, or resected colonic polyps

Amendment 2: Subject has a history of malignancy, except for the following: cancers determined to be cured or in remission for  $\geq 2$  years, curatively resected basal cell or squamous cell skin cancers, cervical cancer in situ, or resected colonic polyps

17. Subject is positive for any of the following:
  - Human immunodeficiency virus (HIV)
  - Hepatitis B surface antigen (HBsAg)
  - Anti-hepatitis C virus antibody (anti-HCV Ab)
18. Subject has an active, clinically significant (CS) infection or evidence of an underlying infection, as manifested by white blood cell count (WBC)  $>$  ULN, and/or fever, in conjunction with clinical signs or symptoms of infection at the time of randomization
19. Subject has any of the following known untreated conditions: proliferative diabetic retinopathy, diabetic macular edema, macular degeneration or retinal vein occlusion (subjects who are already blind may qualify to participate)
20. Subject has had any prior organ transplant (that has not been explanted), or subject is scheduled for organ transplantation (on the waiting list for kidney transplant is not exclusionary)

Amendment 2: Prior organ transplant: subjects who have one of the following conditions or states

  - a) Experienced rejection of transplanted organ within 6 months of transplantation
  - b) Currently on high doses of immunosuppressive therapy (per discretion of the PI)
  - c) Are scheduled for organ transplantation (on the waiting list for kidney transplant is not exclusionary)
21. Subject has participated in an interventional clinical study or has been treated with an investigational drug within 4 weeks prior to screening
22. Subject has drug-treated gastroparesis, short-bowel syndrome, or any other gastrointestinal condition that may lead to reduced absorption of study drug
23. Subject has an anticipated use of dapsone or androgen in any dose amount or anticipated chronic use of acetaminophen or paracetamol  $>$  2.0 g/day during the study

24. Subject has a history of alcohol or drug abuse within 2 years prior to screening  
Amendment 2: Subject has a history of alcohol or drug abuse within 6 months prior to screening
25. Females of childbearing potential, if not practicing complete sexual abstinence or using contraception as detailed in the protocol; male subjects (if not surgically sterile; ie, no vasectomy) with sexual partners of childbearing potential, if not practicing complete sexual abstinence or using contraception
26. Pregnant or breastfeeding females
27. Subject has any medical condition that in the opinion of the Investigator may pose a safety risk to the subject in this study, which may confound efficacy or safety assessment, or may interfere with study participation

Subjects who fail to meet the above eligibility criteria should not, under any circumstances, be randomized or receive study medication. No exceptions to this rule will be allowed. No prospective waiver with regards to eligibility criteria (inclusion/exclusion) will be issued.

### **5.3 Subject Discontinuation and Withdrawal**

The subject is free to permanently discontinue study medication at any time, without prejudice to further treatment. Discontinuation from study medication is not the same as complete withdrawal from the study (ie, withdrawal of consent).

Subjects may withdraw consent and discontinue from the study at any time by discontinuing study medication and refusing to return for any form of follow-up without any prejudice.

A subject who decides to discontinue study medication will always be asked about the reason(s) to discontinue study medication and the presence of AEs (if any). These data will be ascertained and documented by the investigator and recorded in the eCRF as appropriate. The subject should return all study medications.

Reasons for permanent discontinuation of study medication:

- Subject's decision (subject no longer wants to continue study medication (ie, withdrawal of consent))
- Investigator's decision that it is in the best interest of the subject to be withdrawn from the study
- Adverse events
- Significant noncompliance with study procedures, as determined by Investigator or Sponsor
- Lack of efficacy / Meets ESA withdrawal criteria
- Subject is lost to follow-up
- Subject is no longer requiring dialysis due to kidney transplant
- Site terminated by the sponsor

- Pregnancy
- Death

Upon discontinuation from the study, both female subjects of childbearing potential and male subjects with partners of childbearing potential must continue to use a medically acceptable method of contraception for 12 weeks following the last study drug administration.

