#### **4.1.4 Long-term Follow-Up for Premature Treatment Discontinued Subjects**

Subjects who discontinue study medication prematurely will be followed up for vital status, CV events, and hospitalization until study closure, unless consent to participate is withdrawn. Upon completion of EOT and EOS visits, these subjects will be followed up every 3 to 6 month interval (depending on the availability of subjects) until study closure. These visits may occur either in-person or via telephone.

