### 7.2.2 Long-Term Follow-Up of Subjects who Discontinued Study Medication Prematurely

Each subject enrolled in this study is free to permanently discontinue study medication at any time, without prejudice to further treatment. Subject discontinuation and withdrawal are discussed in detail in Section 5.3

Subjects who discontinue study medication prematurely will be followed up for vital status, CV events, and hospitalization until study closure, unless consent to participate is withdrawn. Upon completion of EOT and EOS visits, these subjects will be followed up every 3-6 month interval (depending on the availability of subjects) until study closure. These visits may occur either in-person or via telephone.

The choice of anemia treatment after ET is up to the discretion of the investigator. If the investigator decides to resume ESA treatment in roxadustat treated subjects, the first dose of ESA should be administered at least three days after the last dose of roxadustat.

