AE m and concomitant medication recording	X	X	X	X	X	X	X	X	X	X
Procedure and nondrug therapy recording	X	X	X	X	X	X	X	X	X	X

Abbreviations: Ab = antibody; AE = adverse event; BP = blood pressure; CBC = complete blood count; CHR = reticulocyte hemoglobin content; CV = cardiovascular; ECG = electrocardiogram; ELISA = enzyme-linked immunosorbent assay; EOT = End of Treatment; ET=Early Termination; EOS = End of Study; HbA1c = glycated hemoglobin; HBsAg = hepatitis B surface antigen; hCG = human chorionic gonadotropin; HCV = hepatitis C virus; HD = hemodialysis; HIV = human immunodeficiency virus; HR = heart rate; HRQoL = health-related quality of life questionnaire; hs-CRP = high-sensitivity C-reactive protein; ICF = informed consent form; LFTs = liver function tests; O = optional test/assessment; PE = physical examination; RBC = red blood cell; RR = respiratory rate; TIBC = total iron binding capacity; UIBC = unsaturated iron binding capacity; TSAT = transferrin saturation; WBC = white blood cells; Wk(s) = week(s); X = mandatory test/assessment.

Notes: In subjects on HD, all lab sampling is to be performed prior to the dialysis session.

Subjects who discontinue study medication prematurely will be followed up until the end of the study, unless consent to participate is withdrawn. Upon completion of EOT and EOS visits, these subjects will be followed up every 3-6 month interval for vital status, CV events, and hospitalization (depending on the availability of subjects) until study closure. These visits may occur either in-person or via telephone.

- a All screening procedures should be completed within 6 weeks. For subjects currently taking Mircera®, the screening period can be extended up to 8 weeks.
- b Day 1 is a due treatment date per the existing ESA treatment schedule. All study assessments are to be performed prior to first study drug administration. In subjects on HD study assessments with the exception of HRQoL and body-weight measurement should also be performed prior to or at initiation of dialysis; HRQoL assessments should be done approximately during dialysis (preferably at the beginning) and weight measurement after dialysis.

- c Subjects discontinuing study medication prematurely will complete EOT and EOS. Unless consent is withdrawn, CV events, vital status and hospitalizations will be collected every 3 to 6 months (phone or in-person clinic visit) for these subjects until study closure

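### Protocol 5.3 first separates stopping study drug from withdrawing consent, then equates the two in its list of reasons, which can end follow-up for deaths and CV events in subjects who declined only the drug

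*Protocol*

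**What the plan says.** Protocol 5.3 begins with a clear distinction: "Discontinuation from study medication is not the same as complete withdrawal from the study (ie, withdrawal of consent"). Its next paragraph describes how consent is withdrawn, namely "by discontinuing study medication and refusing to return for any form of follow-up without any prejudice". Both elements are present: stopping the drug and refusing all follow-up.

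The section then says that a subject who stops the drug is asked for the reason, and adds: "These data will be ascertained and documented by the investigator and recorded in the eCRF as appropriate". A list of reasons for permanent discontinuation of study medication follows. Its first entry, the subject's decision, reads "subject no longer wants to continue study medication (ie, withdrawal of consent"). Its second, the investigator's decision, says that "it is in the best interest of the subject to be withdrawn from the study".

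Follow-up after early discontinuation is set out elsewhere. Protocol 4.1.4 says that such subjects "will be followed up for vital status, CV events, and hospitalization until study closure, unless consent to participate is withdrawn". The synopsis, Protocol 7.2.2, Appendix 3 (notes and footnote c) and SAP Section 3 carry the same rule and the same exception. Appendix 3 gives the frequency: "these subjects will be followed up every 3-6 month interval for vital status, CV events, and hospitalization". Section 7.2.2 also sends the reader back: "Subject discontinuation and withdrawal are discussed in detail in Section 5.3".

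**The concern.** The same gloss, withdrawal of consent, is attached to two states that Section 5.3 has just said are different. It falls on the category where the distinction matters most: a subject who has had enough of the tablets or injections but has not refused a telephone call every few months. Withdrawn consent is the stated exception to long-term follow-up, so the label a site gives this subject can decide whether later deaths, MIs and strokes are collected.

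Those events matter. Protocol 3.3 and 9.4.4 make MACE (all-cause death, MI or stroke) the primary safety endpoint for the US submission, to be pooled across studies. Protocol 4.1.2 ties the common closeout to CV events accrued across the dialysis program. The study is open-label: one arm switches to a new oral drug and the other receives an injected ESA of a familiar class. Voluntary stopping could therefore differ by arm, and subjects who choose to stop need not be a random subset. Lost follow-up in this group could be informative as well as incomplete.

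**Working it through.** **The texts side by side**

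| Place | What it implies for a subject who chooses to stop the drug |
|---|---|
| Protocol 5.3, paragraph 1 | Has not withdrawn consent |
| Protocol 5.3, paragraph 2 | Consent is withdrawn only if all follow-up is also refused |
| Protocol 5.3, first listed reason | Has withdrawn consent |
| Protocol 4.1.4, 7.2.2, Appendix 3; SAP 3 | Followed to study closure, unless consent is withdrawn |

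The first two rows cannot be reconciled with the third. Under the first two, the follow-up rule applies. Under the third, its exception applies. No other listed reason fits a subject who simply prefers to stop the drug and will accept contact.

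**Is there another route by which the events would be captured?** Protocol 8.3.1 closes AE and SAE reporting at the visit 4 weeks after EOT or ET. Protocol 8.3.5.2 requires every death during study participation to be reported. After a subject has discontinued or terminated participation, it asks only for deaths and SAEs that may reasonably be related to the study. Once a subject is treated as having withdrawn consent, no planned, unselected source of deaths and CV events remains.

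**Size.** The documents give no rate of stopping by subject decision, so the loss cannot be derived from them. The following is an illustration only.

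Inputs:
- Five-year mortality of 52% in incident renal replacement patients in selected European countries (Protocol 2.1.1).
- Up to 1,200 subjects (Protocol 9.1).
- Assumed: 5% to 15% stop by their own decision, that is 0.05 × 1,200 = 60 to 0.15 × 1,200 = 180 subjects.
- Assumed: 2 years of follow-up remain.
- Assumed: constant hazard, and every such subject is lost.

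Formulas and results:
- Hazard = −ln(1 − 0.52)/5 = 0.147 per year.
- Two-year risk = 1 − exp(−0.147 × 2) = 0.254.
- Deaths unobserved = 60 × 0.254 = 15 to 180 × 0.254 = 46.

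Sensitivity, same method:

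| Five-year mortality | Years remaining | Risk | Deaths (60 to 180 subjects) |
|---|---|---|---|
| 52% (all ages) | 1 | 0.137 | 8 to 25 |
| 52% (all ages) | 2 | 0.254 | 15 to 46 |
| 52% (all ages) | 3 | 0.356 | 21 to 64 |
| 32% (ages 15 to 64) | 2 | 0.143 | 9 to 26 |
| 73% (over 65) | 2 | 0.408 | 24 to 73 |

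The 32% and 73% come from the same sentence of Protocol 2.1.1. Each row assumes the literal reading at every site.

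**The case against.** The best reply is that the plan's intention is not in doubt. Follow-up to study closure is stated in five places, and paragraph 2 of Section 5.3 says what withdrawing consent requires. A parenthetical in a list of reasons for stopping medication need not displace that, and a site that follows the opening paragraphs would keep the subject in follow-up. The eCRF is not among the documents. Nothing shows that this list is the disposition form, or that choosing the reason triggers the end of follow-up. All of this stands. It means that the wording can end follow-up; a reader might infer that it does end it, and the documents do not support that.

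Three other stronger readings also fail:
- A reader might infer that Section 5.3 itself requires follow-up for deaths and CV events. It only implies that follow-up continues; the requirement is in 4.1.4, 7.2.2, Appendix 3 and SAP Section 3.
- A reader might count the investigator-decision entry as a second route to lost follow-up. It is loose wording under a heading about medication, but an investigator's decision is not withdrawn consent and does not meet the exception.
- A reader might take 15 to 46 as the expected loss. Some subjects will genuinely refuse all contact under any wording, and some sites will lose nobody. The mortality figure is for incident European patients, whereas about 150 of up to 1,200 subjects are planned as incident, and the exclusions remove NYHA class III/IV and recent MI or stroke.

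The pooled safety plans are also not available, so how they use events after discontinuation, or censor withdrawn consent, is unknown. No single study is powered for MACE, and the Hb efficacy endpoints do not draw on this follow-up.

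The reply does not remove the contradiction. With up to about 200 centers planned, a text that supports both readings invites uneven practice, and 7.2.2 directs sites to the very section that conflicts.

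**Conclusion.** The contradiction is real and is in current protocol text. Read literally, the list entry moves subjects who declined only the drug into the stated exception to long-term follow-up. Deaths and CV events can then be lost from the US primary safety endpoint, possibly unequally by arm. A difference between arms is plausible in an open-label comparison, but the documents give no data on it.

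The size cannot be calculated from the documents. The 15 to 46 deaths are a worst case that rests on an assumed stopping rate, an assumed 2 years remaining, a proxy mortality figure and literal application everywhere; varying the years remaining or the mortality figure moves the range to between 8 and 73. The conclusion rests on the wording and does not need that figure. Because the wording can change which data are collected, and events missed after contact stops may not be recoverable, this is more than an editorial matter.

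**What to change.** - In Protocol 5.3, delete the parenthetical from the subject's-decision entry and state there that follow-up continues.
- Record withdrawal of consent to follow-up as a separate item with its own date, used only when the subject refuses all follow-up as paragraph 2 of 5.3 describes.
- In the investigator-decision entry, refer to withdrawal from study medication instead of from the study. This is a consistency correction only.
- If the disposition eCRF uses this list, align it and check subjects already recorded under the subject's-decision reason, within the limits of their consent.

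The cost is a short protocol change, a reminder to sites and, if the form is affected, one eCRF option and a set of queries. No visits are added, because contact every 3 to 6 months is already planned. The change leaves the grounds for stopping treatment as they are; it affects only how a stop is recorded and whether contact continues.
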